The SMC will be composed of the principal investigators (PI) of each participating center, the pharmacokinetics (PK) specialist, the medical and safety representatives of the Sponsor and one independent expert in oncology/hematology phase I development. All decisions taken by the SMC and their rationale will be recorded in meeting minutes that will be integrated in the final clinical study report.

Definition of dose limiting toxicities (DLTs)

The DLTs are identical to the events leading to treatment interruption and dose adjustment (see Dose & schedule adaptation), as well as any other unforeseen drug-related AE (including liver function test abnormalities as reported in Dose and Schedule Adaptation) resulting in study drug discontinuation or interruption with/without dose reduction. But only such AEs occurring during cycle 1 (or the first 21 days following the first dosing of OTX015) are considered DLT, except the hematologic DLT for patients with acute leukemia that must be confirmed after 6 weeks of treatment,

Treatment compliance

Patients will record daily in a specific diary, the number of capsules swallowed, time of intake, as well as possible reactions, including vomiting, and their time of occurrence. At each study visit the hospital pharmacist of the study center will provide the patient with the needed number of capsules for the visit interval and retrieve the unused capsules that will be kept until study end for accountability by the study monitor.

Number of subjects

The total number of patients enrolled will depend on the number of DLs explored and of DLT encountered.

Approximately 80 evaluable patients will be enrolled in the dose escalation part (40 by subset acute leukemias/other hematological malignancies)

At least 12 evaluable patients by expansion cohorts will be enrolled in at least 3 expansion cohorts

The total number of evaluable patients is estimated to be 125.

Pharmacokinetics (PK)

Blood collection:

• Once-a-day schedule

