3.2 DEFINITION OF DOSE LIMITING TOXICITIES (DLTS)

DLTs are defined as any of the following treatment-related adverse events occurring in the first cycle (during the first 21 days following study treatment initiation (except hematological toxicity in AL patients confirmed at day 43, see below), regardless of the administration schedule), leading to dose modifications, study treatment interruption or discontinuation, unless a relationship to study medication can be definitely ruled out.

DLTs will be reported immediately to the sponsor using Serious Adverse Events Report Forms (SAERF) with reason for seriousness: "other important medical event" if there is no other reason for seriousness.

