3.2.1 Non-hematological DLTs

- Any grade 3 or 4 non-hematological event (regardless of duration), unless it was not optimally treated with supportive care (e.g. grade 3 vomiting not adequately treated according to antiemetic standard of care).
- Grade 3-4 asymptomatic laboratory abnormal values lasting > 7 days. This definition applies for patients with lab values grade ≤ 1 at baseline. For patients with grade 2 values at baseline, only grade 4 lasting > 7 days will be considered DLT, unless the SMC considers the event clinically significant. See below for liver function tests*.
- Any prolonged grade 2 toxicity (lasting more than 2 weeks) leading to treatment interruption and/or dose reduction

* Any of the following liver test abnormalities** (see Appendix 16.12)

- ALT or $AST > 8 \times ULN$
- ALT or AST $> 5 \times ULN$ for > 2 weeks
- ALT or AST > 3 x ULN AND (total bilirubin > 2 x ULN OR INR > 1.5)
- ALT or AST > 3 x ULN with the appearance of fatigue, nausea, vomiting, right upper quadrant pain or tenderness, fever, rash and/or eosinophilia (> 5%), unless the investigator assesses the rash or fatigue to be related to OTX015 and not related to liver impairment with sponsor's agreement.

**Note: All patients with these liver test abnormalities should be monitored weekly until all abnormalities return to normal or to the baseline state. For patients with isolated total bilirubin increases >2 x ULN or 2 x baseline (if elevated at baseline), except if associated with direct bilirubin \leq ULN, monitoring should be every 2 weeks until bilirubin returns to normal or to the baseline state. Drug induced liver injury (DILI) may develop or progress even after the causative

drug has been stopped. Results should be recorded on the CRF and in the database. See guidelines on the handling of these events (potential Hy's law cases).

Investigators must be warned about qualifying fatigue/asthenia as a DLT. Grade 3 fatigue/asthenia deemed to be related to the study medication is a DLT as per protocol. However, multiple causal events, often intricate, may result in severe fatigue/asthenia in cancer patients participating to a phase I clinical trial, including disease progression, concomitant medications, concomitant medical conditions, anxiety, depression, transportation, etc.

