### Dose & schedule adaptation

Study product dosing (OTX015/MK-8628) will be interrupted in case of: Non-hematologic toxicities:

- any grade 3-4 non hematologic toxicity despite adequate medication, regardless of duration;
- grade 3-4 asymptomatic non hematologic laboratory abnormal values, deemed related to study medication, lasting > 7 days. This definition applies for patients with LFTs/creatinine clearance grade < 1 at baseline. For patients with grade 2 values at baseline, only grade 4 lasting > 7 days will be considered DLT, unless the SMC considers the event clinically significant.
- Any prolonged grade 2 toxicity (lasting more than 2 weeks), leading to treatment interruption and/or dose reduction.

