### Definition of dose limiting toxicities (DLTs)

The DLTs are identical to the events leading to treatment interruption and dose adjustment (see dose & schedule adaptation), as well as any other unforeseen drug-related AE resulting in study drug discontinuation or interruption with/without dose reduction. But only such AEs occurring during cycle 1 (or the first 21 days following the first dosing of OTX015/MK-8628) are considered DLT, except for the hematologic DLT for patient with acute leukemia that must be confirmed after 6 weeks of treatment,

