# **12.3 PRIMARY CRITERION: DOSE LIMITING TOXICITY**

DLTs are defined as any treatment-emergent adverse events (TEAEs) occurring during the first cycle (i.e., the first 21 days following study treatment initiation; note that hypocellular bone marrow and no marrow blasts in AL patients had to be confirmed at day 43), leading to treatment interruption or dose adjustment, or any unforeseen drug-related AE leading to study treatment interruption or discontinuation, unless a relationship to study medication can be definitively ruled out.

The number of patients evaluable for DLT/with DLT in cycle 1 will be tabulated per dose level and overall for safety population.

Type of DLT will be tabulated for patients evaluable for DLT by DL and overall.

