### Non-hematologic DLTs

- Any grade 3 or 4 non-hematologic event (regardless of duration), unless it was not optimally treated with supportive care (e.g. grade 3 vomiting not adequately treated according to antiemetic standard of care).
- Grade 3-4 asymptomatic laboratory abnormal values lasting > 7 days. This definition applies for patients with lab values grade < 1 at baseline. For patients with grade 2 values (liver function test (LFTs) or creatinine clearance) at baseline, only grade 4 lasting > 7 days will be accounted as DLT, unless the SMC considers the event clinically significant.
- Any other AE (such as prolonged and intolerable grade 2 event) resulting in study drug discontinuation or interruption with or without dose reduction

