# **14. CHANGES FROM PROTOCOL**

The protocol allowed for analysis in a per protocol population (section 11.2). This analysis was not performed as it is not appropriate for a phase 1 study with small expansion cohorts.

Overall survival analysis planned in the protocol (section 7.2.2.7) were not performed.

The secondary objectives allowing for assessment of PK/safety, PD/safety and PK/PD relationships were not performed due to insufficient PD data, while PK analyses were not considered pertinent.

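### The third non-hematologic DLT item in SAP 12.3 drops the protocol's 2-week minimum for grade 2 toxicity and the limit on the catch-all, and SAP 14 does not declare it

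*SAP*

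**What the plan says.** The protocol defines DLT twice. Section 3.2 is a closed list: "DLTs are defined as any of the following treatment-related adverse events". It excludes an event only if a link to the drug can be definitely ruled out. Within that list, section 3.2.1 has one grade 2 item: "Any prolonged grade 2 toxicity (lasting more than 2 weeks) leading to treatment interruption and/or dose reduction". It has no catch-all, but it lists specific liver test criteria.

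The protocol synopsis has the same grade 2 item. In its DLT definition it adds a catch-all: "as well as any other unforeseen drug-related AE (including liver function test abnormalities as reported in Dose and Schedule Adaptation"), where the event leads to discontinuation or interruption.

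The SAP's own synopsis follows the protocol synopsis. Its grade 2 item is "Any prolonged grade 2 toxicity (lasting more than 2 weeks), leading to treatment interruption and/or dose reduction" and its catch-all is "as well as any other unforeseen drug-related AE resulting in study drug discontinuation or interruption with/without dose reduction".

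SAP 12.3, which governs the primary analysis, is different. Its third non-hematologic bullet is "Any other AE (such as prolonged and intolerable grade 2 event) resulting in study drug discontinuation or interruption with or without dose reduction". The lead sentence covers cycle 1 treatment-emergent events "leading to treatment interruption or dose adjustment, or any unforeseen drug-related AE leading to study treatment interruption or discontinuation" and keeps the exclusion for events definitively unrelated to the drug. SAP 14 lists three changes from the protocol: no per-protocol analysis, no overall survival analysis, and no PK/PD relationship analyses. The DLT wording is not among them.

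**The concern.** Section 12.3 is the text a programmer would follow for the primary endpoint, and SAP 5 has a second statistician validate that endpoint. The text conflicts with the protocol and with the synopsis in the same SAP. A reader cannot tell whether a short grade 2 event that interrupted dosing is a DLT.

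The definition also feeds the denominator. SAP 8 counts as evaluable any patient who had a DLT, even below 85% of the intended dose. A wider DLT item can therefore add a patient to both parts of the count.

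At stake is the Determination of RD table planned in SAP 16.1. Under Protocol Appendix VIII the SMC validates DLTs, and under Protocol 3.3 it may set one aside for the recommended dose. SAP 12.3 does not say that the table uses the SMC-validated events. If the table were built from the 12.3 text, its counts could differ from those on which the SMC chose the dose.

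**Working it through.** **Side by side**

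| Place | Grade 2 item | Catch-all |
|---|---|---|
| Protocol 3.2 and 3.2.1 | More than 2 weeks, with interruption and/or reduction | None |
| Protocol synopsis | Same | Unforeseen and drug-related; names the listed liver abnormalities |
| SAP synopsis | Same | Unforeseen and drug-related; liver abnormalities not named |
| SAP 12.3, third bullet | Example only, no minimum duration | Any other AE that discontinues or interrupts dosing |

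**Does the lead sentence of 12.3 restore the limits?** It has two arms joined by an *or*. The words on unforeseen, drug-related events sit in the second arm. The first arm is treatment-emergent events that lead to interruption or dose adjustment. At most, then, the limit covers the second arm. The 2-week minimum appears in neither arm.

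**A constructed case.** Protocol 1.1.4 names diarrhea among the toxicities expected at low doses. Suppose possibly related grade 2 diarrhea lasts 5 days in cycle 1 and costs a patient on continuous dosing 5 of 21 daily doses.

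- Dose taken: 16/21 = 76.2%, below 85%.
- Protocol 3.2.1: shorter than 2 weeks, so not a DLT. The patient is non-evaluable and, under Protocol 9, replaced.
- Synopsis catch-all: an expected toxicity is not unforeseen in the ordinary sense, so again not a DLT. This answer is less firm, because the protocol synopsis places already listed liver abnormalities under the same words.
- SAP 12.3, third bullet, read literally: a DLT. SAP 8 then makes the patient evaluable.

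**Where the denominator starts to move.** SAP 8 gives thresholds of 18 days and 12 days, which the 85% rule reproduces:

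- 0.85 × 21 = 17.85, so 18 days are needed: 18/21 = 85.7% passes and 17/21 = 81.0% fails.
- 0.85 × 14 = 11.9, so 12 days are needed: 12/14 = 85.7% passes and 11/14 = 78.6% fails.

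With 1 to 3 missed days of 21, or 1 to 2 of 14, the patient is evaluable under any of the wordings, and only the DLT count can differ. From 4 missed of 21, or 3 of 14, both the DLT count and the number evaluable can differ. These figures cover 21-day and 14-day dosing only. SAP 6.1 also shows 5-7 and 7-21 cohorts among the other malignancies.

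**No rate can be given.** The documents contain no DLT data, so the number of patients affected, if any, is unknown.

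**The case against.** The best defense reads the lead sentence of 12.3 through the SAP synopsis. There, DLTs are the same events that trigger interruption and adjustment under the dose adaptation rules, plus the unforeseen drug-related catch-all. The lead sentence has the same two-part shape and may be a paraphrase of it. Its first arm would then be the listed events, with the 2-week minimum intact. That is a fair reading of the lead sentence, but it does not repair the bullet, which replaces the grade 2 item outright.

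Three stronger readings are tempting, and the documents do not support them.

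- *The SAP definition is wider in every respect.* It is not. The bullet omits dose reduction without interruption, although the lead sentence covers dose adjustment. It still says prolonged, and it adds intolerable. Events definitively unrelated to the drug stay out, as in Protocol 3.2. Much of the catch-all difference is the protocol's own conflict between synopsis and body, which the SAP inherited.
- *The recommended dose is in doubt, because one patient can tip a cohort of 3 or 6.* SAP 5 says the study is complete, and the SAP synopsis gives the dose as established at 80 mg once daily on days 1 to 14 of 21. Rewording the SAP cannot change an escalation decision already taken.
- *DLTs will be derived from the 12.3 text.* The SAP does not say so. Protocol 8.1 provides a DLT box on the SAE form, and the SMC validates DLTs. Silence about the source of the table would, on its own, be only a missing detail.

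It also stands that a discrepancy could be traced. SAP 16.1 plans a listing of cycle 1 DLTs with grade, relationship and action, and a listing of non-evaluable patients with reasons. Protocol 3.3 appends the SMC minutes to the study report.

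**Conclusion.** The inconsistency is real and can be seen from the text alone. The third bullet of SAP 12.3 loses the 2-week minimum and states the catch-all without its limit, contrary to Protocol 3.2.1, the protocol synopsis and the SAP's own synopsis. SAP 14 does not disclose this. Because it is a stated rule for the primary endpoint, it should be corrected and not left to interpretation.

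The size is minor to moderate. The consequence is a possible mismatch between the reported DLT table and the SMC's validated DLTs. It depends on two things the documents do not settle: that the table follows the 12.3 wording, and that at least one patient had a short or foreseeable, possibly related event that interrupted cycle 1 dosing. Which wording the SMC applied is also not shown.

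**What to change.** In SAP 12.3:

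1. Replace the third bullet with the protocol item, "Any prolonged grade 2 toxicity (lasting more than 2 weeks) leading to treatment interruption and/or dose reduction".
2. State the catch-all separately and limit it to other unforeseen, drug-related AEs, as in the synopsis. Carry over the liver criteria of Protocol 3.2.1 at the same time. SAP 12.3 does not list them, so some could be lost once the open item is narrowed.
3. State that the Determination of RD table uses the DLTs validated by the SMC, and mark any that the SMC set aside for the recommended dose.

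In SAP 14, record any departure from the protocol definition that remains.

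The cost is a few sentences of SAP text and a mark in one table. No new data are needed. Applying items 2 and 3 means checking the SMC minutes, which are already due to be appended to the study report.

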# Hematologic DLTs

### Acute leukemia

• Pancytopenia with a hypocellular bone marrow and no marrow blasts lasting for  $\geq 6$  weeks after the start of a cycle. DLT will be suspected in case of pancytopenia with a hypocellular bone marrow and no marrow blast on bone marrow aspiration on day 22, but confirmed on bone marrow aspiration on day 43. Decision of adding or not patients in the cohort will be based on day 22 findings.

# **Other hematologic malignancies**

- Any grade 3 neutropenia, with fever or infection
- Any grade 3 thrombocytopenia with bleeding
- Any grade 4 neutropenia or thrombocytopenia, regardless of symptoms and lasting > 3 days.

# **12.4 ADVERSE EVENTS**

Adverse events occurring or worsening after the treatment start date and before the last study treatment administration date +30 days were considered treatment-emergent adverse events (TEAEs).

- 21 -

Summary AEs (number and % of patients) will be tabulated by DL and overall for patients with:

- at least one treatment-emergent grade 1-5 adverse event (TEAE)
- at least one related treatment-emergent grade 1-5 adverse event (TEAE)
- at least one treatment-emergent grade 3-5 adverse event (TEAE)
- at least one related treatment-emergent grade 3-5 adverse event (TEAE)
- at least one serious TEAE
- at least one serious TEAE related to the study treatment
- a TEAE leading to treatment discontinuation
- a related TEAE leading to treatment discontinuation
- a TEAE leading to death

Tables of individual TEAEs (number and % of patients) grouped by primary System Organ Class (SOC) and Preferred Term (PT; for MedDRA) will be presented by DL and overall. Patients will be counted only once per primary SOC and PT.

These tables will be presented for all cycles as well as for cycle 1 only.

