8.5 PERIOD OF OBSERVATION

For the purposes of this study, the period of observation for collection of AEs extends from the start of treatment with investigational product until the end of study treatment (i.e. 30 days after the last study drug administration), except for adverse events related to study drug, which must be reported during follow-up period until resolution or change of causality from related to non-related or initiation of further antitumor therapy.

If the investigator detects a SAE in a study subject after the end of the period of observation, and considers the event possibly related to prior study treatment, he or she should contact the sponsor to determine how the adverse event should be documented and reported.

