# 6. STATISTICAL METHODOLOGY

# 6.1 GENERAL CONSIDERATIONS

The statistical analysis will be performed by eXYSTAT, under the responsibility of the Sponsor OncoEthix GmbH and the study CRO, OTD, on the basis of the present document.

The statistical analysis will be performed using SAS® software, version 9.4 in a Windows XP operating system environment.

The baseline value is defined as the last available value prior to administration of the investigational product.

The study treatment phase is defined as the period between the date of first administration of investigational product and the date of last administration of investigational product + 30 days.

No replacement of missing values is planned, other than those noted in Section 6.2. Thus the number of patients included in the analyses may vary depending on availability of the parameter considered.

Descriptive statistics will be provided by dose level (DL1 to DL5 or DL6 then expansion cohort, depending on the disease cohort) and overall for each of the two patient cohorts (AL and OHM), and by time point when appropriate, according to the nature of the variable.

- For quantitative variables, descriptive statistics will include: number of missing values, number of observed values, minimum, maximum and median or mean and standard deviation.

- For qualitative variables, descriptive statistics will include: number and percentage of missing values, number of observed values, frequencies and percentages (only for the overall column) per modality.

Calculated statistics and percentages will be displayed with one decimal, unless otherwise specified.

No statistical tests will be performed due to the descriptive nature of this analysis.

In terms of terminology, the mention of "by dose level and overall" will always correspond to the following, according to the cohort:

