### 6.2 HANDLING OF MISSING DATA

In the event of a missing date, replacement will be applied so as to be in the worst case scenario, as follows:

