### For the start date of an adverse event:

Completely missing dates will be estimated as the first treatment administration date.

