# **12. SAFETY EVALUATION**

# **12.1** SAFETY VARIABLES

Safety analyses will be performed in the Safety Population other than for DLT which will be presented in the evaluable for DLT population. All safety data from the study treatment phase will be presented.

Safety data are obtained from clinical and physical examinations, as well as vital signs evaluation.

TEAEs / signs and symptoms of disease observed by the investigator (preferably by the same physician for the same patient) or reported by patients to the study nurses will be recorded and graded according to NCI-CTCAE version 4.03.

Clinically significant laboratory results are those which have clinical consequences. The seriousness, the action taken regarding study medication and patient participation in the study, relation to study medication and the most likely cause, should then be recorded.

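### Read literally, the SAP's TEAE rule leaves out AEs that start on day 1 and do not worsen later, and completely undated AEs that the SAP itself dates to day 1

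*SAP*

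**What the plan says.** **The TEAE rule.** SAP 12.4 takes as treatment-emergent: "Adverse events occurring or worsening after the treatment start date and before the last study treatment administration date +30 days". The summary counts listed there, and the tables by system organ class and preferred term (all cycles and cycle 1 only), are specified in terms of TEAEs.

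**The missing-date rule.** SAP 6.2 opens with "In the event of a missing date, replacement will be applied so as to be in the worst case scenario, as follows". For an AE start date it gives one rule: "Completely missing dates will be estimated as the first treatment administration date".

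**The window elsewhere in the SAP.** SAP 6.1: "The study treatment phase is defined as the period between the date of first administration of investigational product and the date of last administration of" the product plus 30 days. SAP 12.1: "All safety data from the study treatment phase will be presented".

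**The window in the protocol.** Section 8.1 defines a TEAE as something that develops or worsens within the period of observation. Section 8.5 sets that period: "the period of observation for collection of AEs extends from the start of treatment with investigational product", ending 30 days after the last dose.

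**The concern.** An AE that begins on day 1 has an onset date equal to the treatment start date. It is therefore not after that date, and the rule in SAP 12.4 does not count it. The same holds for an AE with no start date at all, since SAP 6.2 moves it to exactly that date. An imputation described as "replacement will be applied so as to be in the worst case scenario" then has the opposite effect: it makes the event non-emergent, which is the favourable classification.

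The safety profile is a secondary objective, and the TEAE tables are its main summary. Day 1 is also when acute effects of the first dose would appear. Patients stay in hospital for at least 8 hours, and the protocol's single-dose volunteer study recorded headaches and gastrointestinal symptoms, although a similar percentage of subjects had AEs on placebo and at 120 mg. An event of this kind that begins on day 1 and resolves without worsening is the kind the rule would miss.

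**Working it through.** The plan states no figure to reproduce. The check is to apply the rule as written to the boundary dates and then compare it with the other definitions.

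**Inputs.** S = date of first administration; L = date of last administration.
- SAP 12.4 as written: S < AE date < L + 30.
- Inclusive rule, the natural reading of SAP 6.1: S ≤ AE date ≤ L + 30.
- SAP 6.2: a completely missing AE start date is set to S.

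| AE date | SAP 12.4 as written | Inclusive rule |
|---|---|---|
| S − 1 | no | no |
| S (day 1) | **no** | yes |
| Completely missing, imputed to S | **no** | yes |
| S + 1 (day 2) | yes | yes |
| L + 29 | yes | yes |
| L + 30 | **no** | yes |
| L + 31 | no | no |

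Of the 21 dates in cycle 1, the rule as written covers 20 and the inclusive rule covers 21. The last date of the 30-day period drops out in the same way as the first.

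**Worsening.** SAP 12.4 also counts worsening, and protocol 8.2 requires a new record when an AE worsens. A day 1 event that worsens on a later date is therefore still captured. What is lost is a day 1 onset without later worsening.

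**Comparison with the rest of the plan.**
- SAP 6.1 and 12.1 start the treatment phase on the first administration date and promise all safety data from it.
- Protocol 8.1 and 8.5 start the TEAE window at the start of treatment.
- SAP 10.4 treats medications ongoing at the first treatment as concomitant, so imputing a start to the first treatment date keeps the medication in. SAP 12.4 has no equivalent wording.
- SAP 14, which lists changes from the protocol, mentions no narrower TEAE window.

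**Size of one lost patient.** Column sizes are from SAP 6.1.
- Escalation columns hold 3 to 8 patients, so a count falls by 1 of 3 to 1 of 8.
- Acute leukemia total: 3+3+4+3+4+8+7+6+7+19+16 = 80; 1/80 = 1.25 percentage points.
- Other malignancies total: 5+3+4+7+6+7+3+5+5+16 = 61; 1/61 = 1.6 percentage points.

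The documents give neither AE counts by day nor a rate of missing dates, so the number of such patients cannot be calculated.

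**The case against.** The strongest reply is that the wording is loose and the intent inclusive. SAP 6.1 and 12.1 and the protocol all include day 1, and the imputation in SAP 6.2 makes sense only if the first treatment date counts as emergent. The programs may already use an inclusive comparison; the dry runs were done and validated. This is a fair account of the probable intent. But it amounts to saying that SAP 12.4 disagrees with everything around it. No passage says that events on the start date count, and the programs are not shown.

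Four stronger conclusions are tempting and are not supported:

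- **That acute reactions vanish from the report.** The by-patient AE listing (SAP 12.4.1) keeps every event, with an emergence field. Vital signs (12.7.1) and the day 1 post-dose ECG comparison (12.7.2) do not depend on TEAE status. Several appendix AE table shells carry no TEAE label, so it is not even clear from them that the filter is applied.
- **That all 141 patients are affected.** That is the number to whom the rule applies. A table row changes only if the patient has no other qualifying event in it, because patients are counted once per organ class and preferred term.
- **That dose-level rates fall by 12.5 to 33 percentage points.** This is 1/8 to 1/3 for one hypothetical patient. SAP 6.1 and 16.1 point to percentages in the total column only, although 12.4 mentions number and percentage by dose level.
- **That the primary endpoint is compromised.** SAP 12.3 does define DLTs using the term TEAE, but it gives its own window of 21 days from treatment initiation. DLTs are reported immediately, validated by the Safety Monitoring Committee, and checked by a second statistician.

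**Conclusion.** The point holds as a defect in a stated rule. Followed as written, SAP 12.4 excludes from the TEAE tables day 1 onsets that do not worsen later and completely undated AEs. It thereby reverses the stated purpose of the imputation and contradicts the SAP's own treatment phase and the protocol's TEAE definition.

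The size is unknown and may be small. The only figures that can be given are the one-patient illustrations above. The conclusion assumes that the tables are programmed from the literal text of 12.4; if the programs already include the start date, only the wording needs correcting. The data themselves are not lost, and the documents do not show that dose decisions relied on this flag.

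**What to change.** Redefine a TEAE in SAP 12.4 as an AE with onset or worsening on or after the date of first administration, up to and including the date of last administration + 30 days. This matches the treatment phase in 6.1. Add two guards:

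1. Exclude a day 1 event only if it is recorded as starting before the first dose. Protocol 8.2 asks for onset time where appropriate, so this can be applied where a time exists.
2. Count an AE with an imputed start date as treatment-emergent unless its end date shows that it ended before the first dose. Without this guard, the inclusive rule would count resolved pre-treatment events.

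The cost is one SAP sentence with these conditions, a check of the comparison in the program, and a rerun of the AE tables. TEAE counts may rise slightly. SAP 6.2 also has no rule for partial AE start dates; that is a separate gap, but it could be closed in the same edit.
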